14 CORRELATIVE STUDIES

Optional Tissue and blood may be collected at the time points notated in the Study Calendar. Samples will be used to identify biomarkers of response or resistance to the prescribed treatments. For those patients with both archival and fresh tissue, comparison between the pre- and post-treatment tissue will be performed as applicable. All correlative tissue collection is optional and not mandatory.

Testing may include, but is not limited to:

- Genomic alterations such as deletions, mutations or amplifications;
- Transcriptome RNA assessments;
- Immunohistochemistry testing for protein expression.
- Cytokine/chemokines
- Circulating free DNA (cfDNA)
- Circulating tumor cells (CTC) detection, enumeration, and characterization

Specimen collection and processing instructions can be found in the lab manual.

14.1 Screening

Archival tissue may be requested for all subjects. Archival tissue slides should not be cut until requested from the Central Lab. Lack of archival tissue will not be exclusionary.

For subjects previously treated with definitive radiotherapy for prostate cancer with molecular imaging (e.g., fluciclovine PET/CT or PSMA PET/CT scan or other per PI discretion)-positive findings at baseline (or less than or equal to one year before study enrollment), a TRUS biopsy may be performed as per institutional standard. Up to 6 cores from the TRUS biopsy may be obtained for correlative studies.

14.2 Oligometastasectomy and/or Prostatectomy

For subjects undergoing oligometastasectomy and/or salvage prostatectomy, 2 sections of tissue may be collected from the prostate and each of the lymph node dissection if available after SOC tissue collection.

14.3 Blood Correlative Studies

Up to 20 mL of blood may be collected at each time point. Instructions for processing and shipping will be detailed in the lab manual.

15 ETHICAL AND REGULATORY CONSIDERATIONS

15.1 Informed consent

Informed consent will be obtained from all research participants prior to performing any study procedures using the most recent IRB-approved version.

15.2 Human Subjects Protections

15.2.1 Participation of Children

Subjects must be at least 18 years of age to participate.

15.2.2 Participation of Subjects Unable To Give Consent

Subjects must be able to provide informed consent and willing to sign an approved consent form that conforms to federal and institutional guidelines.

15.3 Institutional Review

This study will be approved by the Institutional Review Board of the University of Utah.

15.4 Data and Safety Monitoring Plan

A Data and Safety Monitoring Committee (DSMC) is established at Huntsman Cancer Institute (HCI) to ensure the well-being of subjects enrolled on Investigator Initiated Trials that do not have an outside monitoring review. The roles and responsibilities of the DSMC are set forth in the NCI-approved Data and Safety Monitoring (DSM) plan. The activities of the committee include reviewing adverse events (including SAEs), deviations, important medical events, significant revisions or amendments to the protocol, and approving cohort/dose escalations. If the DSMC and/or the PI have concerns about unexpected safety issues, the study will be stopped and will not be resumed until the issues are resolved. The DSMC also reviews and approves audit reports generated by the Research Compliance Office.

This study is classified as moderate risk per the NCI-approved DSM plan.

Each moderate risk study may be assigned a physician member of the DSMC as medical monitor, or in rare cases, an external medical monitor. The medical monitor will be notified of all serious adverse events (SAEs). SAEs occurring in subjects treated at HCI or its affiliates will also be reviewed by the full DSMC monthly. The full committee will also review all toxicities for subjects on treatment and within 45 days of their last treatment on a quarterly basis.

Each moderate-risk study will be assigned a dedicated research compliance officer who will monitor the trial. Moderate-risk trials will be monitored by RCO personnel after the first subject is enrolled and every six months thereafter during active enrollment. The RCO

monitor will review the study status and summarize enrollment, toxicities, SAEs, dose escalation, statistical endpoints (e.g., stopping rules), deviations, etc. for the full DSMC membership at the regularly scheduled meetings. Amendments that increase risk, change dosing, or impact study objectives will be reviewed by the DSMC and approved by the PRMC and IRB. Moderate-risk trials will be formally reviewed by the DSMC after the first subject is enrolled and then semi-annually thereafter.

An initial audit of moderate-risk studies will be conducted by the RCO approximately one year after enrollment begins and annually thereafter. Audits of moderate-risk studies may be conducted more frequently as requested by the DSMC, IRB, PRMC, RCO management, or the PI.

15.5 Adverse Events and Serious Adverse Events

This study will utilize the CTCAE (NCI Common Terminology Criteria for Adverse Events) Version 5.0 for AE and SAE reporting.

In addition, the Clavien-Dindo classification will be used to evaluate surgical complications.

15.5.1 Adverse Events (AEs)

An adverse event is the appearance or worsening of any undesirable sign, symptom, or medical condition occurring after starting the study treatment even if the event is not considered to be related to study treatment. For the purposes of this study, the terms toxicity and adverse event are used interchangeably. Medical conditions/diseases present before starting study salvage treatment are only considered adverse events if they worsen after starting study salvage treatment. Abnormal laboratory values or test results constitute adverse events only if they induce clinical signs or symptoms, are considered clinically significant, or require therapy.

Collection of adverse events will begin with the first study salvage treatment (surgery OR radiotherapy for bone metastases) and end 1 year after the last study treatment (including palliative radiotherapy if applicable) or until a new cancer treatment is initiated.

Information about all adverse events, whether volunteered by the subject, discovered by investigator questioning, or detected through physical examination, laboratory test or other means, will be collected and recorded and followed as appropriate.

The occurrence of adverse events should be sought by non-directive questioning of the subject at each visit or phone contact during the study. Adverse events also may be detected when they are volunteered by the subject during or between visits or through physical examination, laboratory test, or other assessments. As far as possible, each adverse event should be evaluated to determine:

1. The severity grade based on CTCAE v5 (grade 1-5)
2. Its relationship to the study treatments(s) (definite, probable, possible, unlikely, not related)
3. Its duration (start and end dates or if continuing at final exam)
4. Action taken (no action taken; study salvage treatment dosage adjusted/temporarily interrupted; study salvage treatment permanently discontinued due to this adverse

event; concomitant medication taken; non-drug therapy given; hospitalization/prolonged hospitalization)

5. Whether it constitutes an SAE

All adverse events will be treated appropriately. Such treatment may include changes in study salvage treatment as listed in the dose modification section of this protocol (see section 8 for guidance). Once an adverse event is detected, it should be followed until its resolution, and assessment should be made at each visit (or more frequently, if necessary) of any changes in severity, the suspected relationship to the study salvage treatment, the interventions required to treat it, and the outcome.

All adverse events will be immediately recorded in the subject research chart.

15.5.2 Serious Adverse Event (SAE)

Information about all serious adverse events will be collected and recorded. A serious adverse event is an undesirable sign, symptom or medical condition which:

- Is fatal or life-threatening
- Results in persistent or significant disability/incapacity
- Is medically significant, i.e., defined as an event that jeopardizes the subject or may require medical or surgical intervention to prevent one of the outcomes listed above
- Causes congenital anomaly or birth defect
- Requires subject hospitalization or prolongation of existing hospitalization, unless hospitalization is for:
 - Routine treatment or monitoring of the studied indication, not associated with any deterioration in condition (procedures such as central line placements, paracentesis, pain control)
 - Elective or pre-planned treatment for a pre-existing condition that is unrelated to the indication under study and has not worsened since the start of study salvage treatment
 - Treatment on an emergency outpatient basis for an event not fulfilling any of the definitions of a SAE given above and not resulting in hospital admission
 - Social reasons and respite care in the absence of any deterioration in the subject's general condition

Collection of serious adverse events will begin at the time of salvage treatment and end 1 year after the last dose of study treatment or until a new cancer treatment is initiated, whichever happens the soonest.

Any death from any cause while a subject is receiving treatment on this protocol or up to 365 days after the last dose of protocol treatment will be reported. Any death which occurs up to 3 years after protocol treatment has ended but which is felt to be treatment related, must be reported.

Toxicities which fall within the definitions listed above must be reported as an SAE regardless if they are felt to be treatment related or not. Toxicities unrelated to treatment that do NOT fall within the definitions above, must simply be documented as AEs in the subject research chart.

15.6 SAE Reporting Requirements

SAEs must be reported to the DSMC, the FDA, and the IRB according to the requirements described below:

A MedWatch 3500A form must be completed and submitted to [contact] as soon as possible, but no later than 1 working day of first knowledge or notification of event.

DSMC Notifications:

An HCI Research Compliance Officer (RCO) will process and submit the MedWatch form to the proper DSMC member as necessary for each individual study.

The RCO will summarize and present all reported SAEs according to the Data and Safety Monitoring Plan at the monthly DSMC meeting.

FDA Notifications:

Adverse events occurring during the course of a clinical study that meet the following criteria will be promptly reported to the FDA:

- Serious
- Unexpected
- Definitely, Probably or Possibly Related to the investigational treatment
- Fatal or life-threatening events that meet the criteria above will be reported within 7 calendar days after first knowledge of the event by the investigator; followed by as complete a report as possible within 8 additional calendar days.

All other events that meet the criteria above will be reported within 15 calendar days after first knowledge of the event by the investigator.

The RCO will review the MedWatch report for completeness, accuracy and applicability to the regulatory reporting requirements.

The RCO will ensure the complete, accurate and timely reporting of the event to the FDA.

The Regulatory Coordinator will submit the report as an amendment to the IND application.

All other adverse events and safety information not requiring expedited reporting that occur or are collected during the course of the study will be summarized and reported to the FDA through the IND Annual Report.

IRB Notification:

Events meeting the University of Utah IRB reporting requirements (<http://www.research.utah.edu/irb/>) will be submitted through the IRB's electronic reporting system within 10 working days.

15.7 Reporting of Pregnancy

Although pregnancy is not considered an adverse event, it is the responsibility of investigators or their designees to report the pregnancy of a male subjects' female partner as an SAE. Pregnancies or lactation that occurs during the course of the trial or with 45 days of completing treatment or starting another new anticancer therapy, whichever is earlier, must be reported to the DSMC, IRB, FDA, and the sponsor as applicable. All female partners who become pregnant must be followed to the completion/termination of the pregnancy. Pregnancy outcomes of spontaneous abortion, missed abortion, fetal death, intrauterine death, miscarriage and stillbirth must be reported as serious events.

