5.1 Inclusion Criteria

Yes/No (Response of "no" = subject ineligible)

5.1.1 _____ Male subjects age \geq 18 years.

5.1.2 _____ Histologically proven adenocarcinoma of the prostate.

5.1.3 _____ Recurrent prostate carcinoma after definitive therapy for primary disease defined as:

- Post-prostatectomy (with/without adjuvant radiotherapy): Patients must have a detectable or rising PSA level that is >0.05 ng/mL, with a second confirmatory level that is >0.05 ng/mL after a minimum of 1 week.
- Post radiotherapy/ablation (without radical prostatectomy): PSA rise ≥ 2 ng/mL over nadir.

5.1.4 _____ Subjects treated with prior definitive radiotherapy for prostate cancer who have positive molecular imaging (e.g., fluciclovine PET/CT or PSMA PET/CT scan or other per PI discretion) suggesting recurrent intraprostatic disease must undergo TRUS biopsy less than or equal to one year before study enrollment:

- If the TRUS biopsy is negative, no additional treatment is required to the prostate in addition to that of scan-positive sites.
- If the TRUS biopsy is positive, subject must undergo salvage prostatectomy or salvage radiotherapy to the primary site concurrently with the study treatment per the treatment protocol algorithm.
- Note: Biopsy is not required for prostate fossa recurrences after radical prostatectomy.

5.1.5 Oligometastatic disease defined as 10 or fewer metastatic lesions to lymph nodes and/or bones only.

5.1.6 For patients with oligometastatic disease involving lymph nodes, metastasis is confined to the pelvic or para-aortic (below IMA) regions on molecular imaging (e.g., fluciclovine PET/CT or PSMA PET/CT scan or other per PI discretion).

5.1.7 All subjects must be surgical candidates if surgery is indicated per the treatment algorithm.

5.1.8 ECOG Performance Status ≤ 2 .

5.1.9 Use of condoms for male subjects who have not had surgical removal of their prostate and have a partner of child bearing potential beginning at the time of ICF signature and lasting until at least 6 months after the last radiation treatment. Because of the potential side effect on spermatogenesis associated with radiation, female partners of childbearing potential must agree to use a highly effective contraceptive method during and for 6 months after completing treatment.

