7.3 Contraception

Subjects who have not had surgical removal of their prostate and have a partner of child bearing potential must agree to use condoms beginning at the signing of the ICF until at least 6 months after the last dose of study treatment. Because of the potential side effect on spermatogenesis associated with radiation, female partners of childbearing potential must agree to use a highly effective contraceptive method during and for 6 months after completing treatment.

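### The partner-pregnancy reporting window in section 15.7 is not reconciled with the 6-month contraception period or the 1-year SAE window, and it leaves a gap for men who start new anticancer therapy

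*Combined protocol and SAP*

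**What the plan says.** Section 15.7 first says that pregnancy is not an adverse event. It then makes the investigator responsible, with no date attached, to "report the pregnancy of a male subjects' female partner as an SAE". The next sentence sets the mandatory scope in two limbs: "Pregnancies or lactation that occurs during the course of the trial", and those arising "with 45 days of completing treatment or starting another new anticancer therapy, whichever is earlier, must be reported". The protocol does not define the trial period meant in the first limb. The section goes on to require that every pregnant partner be followed until the pregnancy ends. It lists pregnancy losses and stillbirth as outcomes to be reported as serious; congenital anomaly is not on that list.

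Section 15.5.2 does list it as an SAE criterion ("Causes congenital anomaly or birth defect"), but SAE collection is to "end 1 year after the last dose of study treatment or until a new cancer treatment is initiated, whichever happens the soonest".

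On contraception, criterion 5.1.9 has condom use "lasting until at least 6 months after the last radiation treatment", while section 7.3 has it "until at least 6 months after the last dose of study treatment". Both places add that "female partners of childbearing potential must agree to use a highly effective contraceptive method during and for 6 months after completing treatment", and both give a possible radiation effect on spermatogenesis as the reason.

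Section 6.4.2 takes a subject off study when new anti-cancer therapy starts. Sections 4.4 and 9.3 otherwise provide follow-up for up to 3 years, with visits every 3 months.

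**The concern.** The protocol names a reproductive risk and asks couples to guard against it for 6 months after treatment. The section that should detect failures of that precaution names a post-treatment limit of 45 days, and it also points to two longer periods without saying which applies. A site that learns of a partner pregnancy conceived in month 4 cannot tell from the text whether it must be reported.

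New anticancer therapy sharpens the problem. It is an expected event here: time to ADT is a secondary endpoint, and section 6.2.3.3 gives no further study treatment to men whose PSA falls by less than one third. For an irradiated man, starting ADT does not change the radiation already received, yet it closes the dated reporting routes. What is at stake is capture of a rare but serious safety outcome. No efficacy endpoint is involved.

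**Working it through.** The plan gives no figure to reproduce here, so the check sets the windows side by side and then does simple arithmetic.

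**1. The windows**

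| Source | Period after treatment | Ended by new therapy? |
|---|---|---|
| 15.7, opening duty | none stated | not stated |
| 15.7, first limb | trial period, undefined | yes, if being off study (6.4.2) ends it |
| 15.7, second limb | 45 days | yes, if new therapy is read as the earlier end date |
| 15.5.2, SAE collection | 1 year | yes |
| 5.1.9 and 7.3, contraception | 6 months | no |

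**2. Share of the contraception period outside the 45-day clause**

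Let D be the contraception period in days. The uncovered share is 1 − 45/D. The documents state months, so D is an assumption: 182.6 days at 30.44 days per month, with a range of 168 to 184.

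- D = 182.6: covered 45/182.6 = 24.6%; uncovered 182.6 − 45 = 137.6 days, or 75.4%.
- D = 168: uncovered 123 days, 73.2%.
- D = 184: uncovered 139 days, 75.5%.

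If new therapy starts on day 0, 15 or 30 and closes the clause at once, the uncovered share is 100%, 91.8% or 83.6%. The clause can also be parsed as 45 days from the earlier of the two dates. Therapy started after treatment completion then does not shorten it, and the 75% figure stands.

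**3. The same share on the wider readings**

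If the trial period includes the 3-year follow-up, or if the 1-year SAE window governs, all 6 months are covered and the uncovered share is 0%. This holds only for men who start no new therapy.

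**4. Men who start new therapy within the 6 months**

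The 45-day clause has closed by day 45 at the latest, SAE collection ends, and the man is off study. What remains is at most the undated opening duty in 15.7. For example, with therapy started at month 2, 6 − 2 = 4 months of the contraception period remain with no dated reporting duty.

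**5. Congenital anomaly**

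Assume a 9-month pregnancy. A conception at month 3 delivers at 3 + 9 = 12 months, which is the end of SAE collection. A conception at month 6 delivers at 6 + 9 = 15 months, which is 3 months past it. An anomaly found at birth after a conception later than about month 3 is therefore outside the only provision that names it.

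**6. Condom-period anchor**

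Criterion 5.1.9 counts from the last radiation treatment, and 7.3 counts from the last dose of study treatment. For a man treated by surgery alone, the first anchor gives no date. Where bone radiotherapy precedes surgery, as section 6.2 allows, the two anchors fall on different dates.

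**The case against.** A reader might infer that partner pregnancies are reportable only to day 45 and that later ones are neither monitored nor followed to outcome. The documents do not support that. The sentence containing the 45-day clause also covers pregnancies during the trial, and follow-up runs for up to 3 years. The pregnancy is classed as an SAE, and a pregnancy known before month 12 falls within SAE collection if no new therapy has begun. Follow-up of pregnant partners to the end of pregnancy is already required with no time limit, so a delivery at month 15 matters only for the anomaly outcome.

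It could be answered that the wide reading leaves the 45-day limb with nothing to do. That is not quite so: a man who withdraws soon after treatment is no longer in the trial, and for him the limb extends reporting. The narrow reading nevertheless has some support, because section 15.4 also uses 45 days after last treatment for committee review of toxicities. Neither reading is settled by the text.

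Two further objections carry weight. The protocol states a contraception period, not a risk window; treating the two as the same is a reasonable inference, and different lengths for different functions are not in themselves a contradiction. The new-therapy cut-off is also applied consistently across 6.4.2, 15.5.2 and 15.7, so extending reporting past it is a choice for the sponsor. What stands after these objections is the lack of a governing rule, the gap for men who start new therapy, and the missing anomaly outcome.

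**Conclusion.** The point holds as an internal inconsistency in safety reporting. The uncovered part of the contraception period is about 75% (73.2% to 75.5%) if the 45-day clause governs, and 0% if either wider reading governs and no new therapy starts. For men who start new anticancer therapy within the 6 months, some of the period is without a dated reporting duty on every reading.

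These shares are shares of calendar time, not of expected pregnancies. They rest on the assumed conversion of months to days and on taking the contraception period as the relevant exposure window. The anomaly point also assumes a 9-month pregnancy.

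Severity is minor. The trial enrols 20 men, few events are likely, and the documents give no pregnancy rate from which to put a number on them. No efficacy estimate, confidence interval or sample size is affected. The case for acting is that the change is small and the outcome, if it occurs, is serious.

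**What to change.** Reconcile 15.7 with 5.1.9, 7.3, 15.5.2 and 6.4.2:

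- State in 15.7 that any partner pregnancy conceived from the start of study treatment to the end of the protocol's own contraception period is reportable, including after new anticancer therapy starts. This replaces the undefined trial period and the 45-day clause with one rule.
- Add congenital anomaly to the outcomes reported under 15.7, whatever the status of the SAE window. The existing follow-up to the end of pregnancy can stay as it is.
- Reconcile the condom-period anchor between 5.1.9 and 7.3. Which anchor applies is for the investigators to decide.

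The cost is a sentence or two in 15.7 and a matching edit to one contraception section. Men still on study need no added visit, since the 3-monthly visits fall within the 6 months. Men taken off study for new therapy have no scheduled visits, so they need either one brief contact near the end of the contraception period or a written instruction to self-report.
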